- To assess whether a Multicomponent Discharge Transition Intervention reduces the risk of early readmission compared to a control group following standard treatment.

- Secondary**

- To check whether the risk of early readmission is reduced with respect to the previous year in the experimental group and in the control group.

- To check whether early readmission rates are reduced in the experimental group compared with the control group and with respect to readmission rates in the previous year.

- Identify risk factors that are associated with early readmissions.

- To test whether a scale for estimating the risk of early readmission has adequate psychometric characteristics for such estimation.

- To test whether a Post-Discharge Recovery Support Psychotherapy Group improves outcome on measures of recovery, functioning, subjective well-being, social support, and satisfaction with mental health treatment in patients at high risk of early readmission.

- To test whether the Transition to Discharge intervention also reduces the risk of frequent readmission (revolving door).

- **Design**

The present study is a quasi-experimental cluster clinical trial aimed at assessing the efficacy of a multicomponent discharge transition program for the reduction of early readmissions in a MHHU. The development of this study consists of two distinct parts or elements:

To carry out the main objective, a quasi-experimental design with a control group will be used, and within the intervention, an early readmission risk assessment scale will be created to categorize patients into different risk levels.

In addition, a study will be conducted to assess the predictive value and validity of the early readmission risk rating scale and to study the risk factors for early readmission.

- **Setting**

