- Symptom Management and Coping Resources: This involves promoting recognition of the clinical condition, facilitating awareness about the origin of distress, its course, and typical ways of expression, fostering self-awareness and self-management. The relationship with the symptom, its acceptance, and pharmacological management will be addressed, along with recognition of prodromes, self-care habits, and crisis management.
- Family intervention: Four multi-family sessions will be carried out on a monthly basis in an integrated manner. They will be mainly based on the optimization of communication strategies in the family environment and management of crisis situations.
- Values orientation and commitment to meaningful activities: The therapeutic approach is focused on achieving greater subjective well-being and attaining a more satisfying and meaningful life, always from a recovery-oriented and person-centered model.
- Relapse prevention: Anticipation of possible scenarios, detection of potential risks and implementation of effective coping strategies. Strategies aimed at enhancing self-control, self-efficacy and self-determination, through the joint development of safety plans and the enhancement of personal strengths.

Other aspects that will be addressed throughout the therapeutic process include emphasis on the therapeutic bond, group cohesion, strengthening social and family ties, peer support, and learning in the here and now of the group reality.

Control group

To assess the effectiveness of the Multicomponent Discharge Transition Program, users from Málaga East Axarquía Hospital and North Málaga Health Management Area will be employed as the control group. Participants in the control group will continue with their usual treatment.

Additionally, users from the Mental Health Management Unit of Regional Hospital of Málaga who were admitted the previous year and thus did not participate in the intervention program will also be used as a control group.

- **Participants and recruitment**

For the development of the present study, data from all hospital admission episodes at MHHU during the 12 months following the implementation of the Discharge Transition Intervention Program will be considered. Similarly, data from all users who have experienced any hospital admission episodes at UHSM in the year prior to the intervention will also be utilized.

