The experimental group, to which the Discharge Transition Intervention Program will be applied, will consist of users whose Community Mental Health Units (CMHU) are affiliated with the Regional Hospital of Málaga. Users belonging to other hospitals in the province will be excluded from the intervention program and will form part of the control group.

Participants included in the Post-Discharge Group Psychotherapy Support Recovery Program will be those at high risk or with an early rehospitalization already occurred, who also meet the inclusion criteria. The relevance of their inclusion will be assessed through a clinical interview by the Specialist in Clinical Psychology in charge of the program, following these criteria.

Inclusion criteria:

- Be of legal age.
- Speak spanish fluently.
- Have had recent admission to the MHHU of the Regional Hospital of Málaga and a score considered as "High Risk" on the Early Rehospitalization Risk Scale or have experienced an early rehospitalization.
- Belong to the Clinical Management Unit of Mental Health of the RUH of Málaga.
- Have sufficient cognitive capacity to understand the rules and contents of the group intervention.

Exclusion criteria:

- Individuals whose primary diagnosis is a Mental and Behavioral Disorder due to psychoactive substance use.
- Moderate or severe intellectual disability.
- Clinical Management Unit belonging to a hospital other than the RUH of Málaga.
- Lack of commitment to attending sessions or complying with group rules.

- **Study variables**

Main outcome variables

The main outcome variable will be the risk of early reentry of the experimental group compared to the control group, which did not follow the intervention.

Secondary outcome variables

The risk of early rehospitalization of the admission episodes from the experimental group will be compared to the risk of early rehospitalization of admission episodes from the previous year.

Frequent rehospitalization will be assessed as having undergone at least two readmissions within a 6-month follow-up period. The risk of frequent rehospitalization will be considered as a secondary variable.

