In the analysis for the creation of the early rehospitalization risk scale, a univariate logistic regression analysis will be used. For the final selection of factors, a forward stepwise multivariate analysis will be performed, introducing variables with greater statistical significance. Finally, a scale will be developed to measure the risk of early rehospitalization in each admission episode, whose sensitivity and specificity will be tested beforehand using a receiver operating characteristic (ROC) curve. The construction of the scale will follow the procedure outlined in detail in Sullivan et al. (23).

To evaluate the differences between the intervention group and the control groups, a univariate and multivariate mixed logistic regression analysis will be conducted, introducing potential confounding variables (unit occupancy, age, sex, and the variables used in the scale for estimating the risk of early rehospitalization). To assess potential differences in Core Om, Duke-unk-11, PSP, and QPR among patients participating in the Post-Discharge Recovery Support Psychotherapy Program, the paired Student's t-test for repeated measures or the non-parametric Wilcoxon signed-rank test for a single sample will be used.

DISCUSSION

The present research study aims to analyze the risk factors for early rehospitalization of patients discharged from a short-term psychiatric hospitalization unit. Based on this information, the goal is to stratify the risk and direct more intensive therapeutic measures to those individuals with a higher likelihood of rehospitalization to reduce early rehospitalization rates.

Thus, determining the risk of psychiatric rehospitalization for individual patients is a critical step in efforts to address the potentially avoidable high rate of this negative outcome, as highlighted in the READMIT study (4). This study conducted in Canada succeeded in providing a framework to identify patients at high risk of rehospitalization through the development of a prognostic index with moderate discriminative capacity.

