One of the main strengths of our study is that it will be conducted in a real-world context, and the instrument to be used for patient stratification will be developed in the same population where it will subsequently be applied, reducing the possibility of cultural factors or context-specific factors biasing the validity of the risk scale. Additionally, the individuals involved in the care of hospitalized patients will work directly on this instrument and subsequently on the intervention to be developed, which will consist of multiple components.

Among the challenges of the study are being able to fulfill all the measures outlined in the intervention program, as external factors may condition it: shortage of hospital beds, premature discharges or voluntary discharges, staffing deficits, lack of community resources, etc. Additionally, many factors associated with early rehospitalization may be difficult to address within the program itself: substance abuse, homelessness, difficulties associated with group work, cognitive deficits, heterogeneity of participating subjects, etc.

One of the major limitations of the study is that it will only be conducted in one inpatient unit, so generalization of the results to other settings will be problematic. As reflected in previous studies, such as the one cited above, its findings have not been able to effectively discriminate potentially readmitting patients in subsequent studies conducted with different populations (24). This tells us about the complexity of the phenomenon of early readmission, an event that is difficult to predict, multicausal and involves factors that require a complex approach (25).

Finally, an important aspect is that the treatment allocation is not randomized, which may introduce biases that will be addressed by using two control groups. However, there may potentially be confounding variables that will be considered in the analysis. Given these limitations, if this study yields satisfactory results, a likely future direction could be to develop a randomized, multicenter clinical trial at the regional or state level.

LIST OF ABBREVIATIONS

CAT: Client's Assessment of Treatment
CMHU: Community Mental Health Unit
CPG: Clinical Practice Guidelines
CTI: Critical Time Interventions
MHHU: Mental Health Hospitalization Unit
PDC: Provincial Drug Dependency Center
PSP: Personal and Social Performance Scale
QPR: Recovery Process Questionnaire
RUH: Regional University Hospital

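### With one treated and two control areas and no stated random effects, standard p-values and intervals from the mixed logistic model are too optimistic whenever areas vary

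*Combined protocol and SAP*

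**What the plan says.** - Design: "The present study is a quasi-experimental cluster clinical trial aimed at assessing the efficacy of a multicomponent discharge transition program".
- Participants and recruitment: the experimental group "will consist of users whose Community Mental Health Units (CMHU) are affiliated with the Regional Hospital of Málaga". This is one catchment area.
- Control group: "users from Málaga East Axarquía Hospital and North Málaga Health Management Area will be employed as the control group". These are two catchment areas. Regional Hospital users "who were admitted the previous year and thus did not participate in the intervention program will also be used as a control group".
- Study variables: "The main outcome variable will be the risk of early reentry of the experimental group compared to the control group". The comparison with the previous year is secondary.
- Data analysis: "a univariate and multivariate mixed logistic regression analysis will be conducted, introducing potential confounding variables". The confounders listed are unit occupancy, age, sex and the risk-scale variables.
- Discussion: the study is limited because "it will only be conducted in one inpatient unit". The text ties this to generalisation. A later paragraph accepts that non-random allocation may bias the result and offers two control groups and confounder adjustment in response.

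The documents do not name the grouping variable for the random effects, an area or period term, an ICC, a significance level, or a method for a small number of clusters.

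**The concern.** The programme is given to an area, so the area is the unit that differs between the arms. One treated area gives no replication in that arm. Whatever else distinguishes its readmission risk in the programme year enters the estimate as programme effect. The plan itself points to such sources: the Introduction lists community resources after discharge among the institutional factors linked to readmission, and the Discussion names staffing deficits and lack of community resources. The listed covariates do not remove this, because they are the occupancy of one shared ward plus patient and episode characteristics.

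An interval that reflects only the sampling of episodes or patients is then too narrow, and an ordinary difference between areas can be reported as an effect of the programme. This bears on the primary comparison.

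**Working it through.** The plan gives no sample size, power or alpha, so there is no design figure to reproduce. A two-sided 5% test is assumed.

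**Inputs (Setting section, 2022).** Admissions 838; 30-day readmission 15.08%; reference populations 336,968 (treated), 150,823 and 109,958 (controls), which sum to the stated 597,749.

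**Assumptions.** Episodes split by population share (56.4%, 25.2%, 18.4%), giving about 472 / 211 / 154; common risk p = 0.1508, so p(1−p) = 0.128; independent episodes; no covariate adjustment.

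**1. Episode-level SE of the log odds ratio.** Variance = 1/(472 × 0.128) + 1/(366 × 0.128) = 0.0379, so SE = 0.195.

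**2. Adding area variation.** If area log odds have SD τ, the variance rises by τ²(1 + Σw²), where w are the two control-area shares of control episodes: 0.578² + 0.422² = 0.512. Real error of the nominal 5% test = 2[1 − Φ(1.96 × 0.195 / SE_total)].

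| τ | ICC = τ²/(τ² + π²/3) | Total SE | Real error |
|---|---|---|---|
| 0.05 | 0.0008 | 0.204 | 6.2% |
| 0.1 | 0.003 | 0.230 | 9.8% |
| 0.2 | 0.012 | 0.314 | 22.4% |

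One SD around 15.08% is a risk of 13.8–16.4% at τ = 0.1 and 12.7–17.8% at τ = 0.2.

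**3. Allowing for repeat admissions.** With an illustrative design effect of 1.5, the model variance is 1.5 × 0.0379 = 0.0568. The same formula gives 8.2% at τ = 0.1 and 17.3% at τ = 0.2.

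**4. Which random effect?**
- *Patient.* It accounts for repeat admissions but carries no area variation.
- *Community unit.* This adds clusters, but variation shared by all units of one area stays outside the error term.
- *Area.* The treated area is fitted by the treatment term, so the variance rests on the difference between two control areas, with 1 degree of freedom. The sampling variance of that difference is 1/(211 × 0.128) + 1/(154 × 0.128) = 0.088. The chance that REML returns zero is 2Φ(√[0.088/(0.088 + 2τ²)]) − 1: 63% at τ = 0.1 and 53% at τ = 0.2. In a simulation under no effect (500 data sets per setting; maximum likelihood, area random intercept, Wald test), the estimated variance was near zero in 94% and 89% of data sets at ICC 0.005 and 0.01. Real error was about 10% and 20%, with Monte Carlo error of about 2 percentage points.

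**5. Using both years.** A treated-area-by-year contrast cancels stable area differences. With equal yearly numbers its SE is √(2 × 0.0379) = 0.275. Area-by-year variation of SD σ adds 2σ² × 1.512, giving 0.289, 0.326 and 0.444 at σ = 0.05, 0.1 and 0.2. The data cannot estimate σ usefully: six area-year cells less five parameters (three areas, one year, one interaction) leave 1 residual degree of freedom.

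**The case against.** The strongest reply is that the plan never says area variation is left out. It calls the model mixed and leaves the random effects open. That is correct: a reader might infer that the model ignores areas, but the text supports only that the structure is unspecified. The point survives because none of the three structures in the working captures area variation reliably.

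Second, the size is assumed. All three areas share one inpatient unit and the model adjusts for case mix, so area variation could be small; at SD 0.05 the error is barely above nominal. This stands. The figures are a sensitivity range, and the statement that the test fails to hold 5% is conditional on non-zero area variation.

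Third, the Abstract and the secondary aims already bring in the previous year for both groups, and the Discussion concedes non-random allocation. This also stands, and it makes the repair small. But no area-by-period term is specified, the primary outcome remains experimental versus control, and the limitations address bias and generalisation rather than precision.

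Fourth, one may treat the three areas as fixed and regard their differences as confounding rather than variance. That is a legitimate framework. The interval is then conditional on these areas, and the plan should say so.

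**Conclusion.** The concern holds in a conditional form. In the concurrent comparison the programme effect and the treated area's own deviation cannot be separated, and no choice of random effect repairs this with three areas. Standard p-values and intervals are too optimistic to an extent the documents cannot settle: about 6%, 10% and 22% real error at area SDs of 0.05, 0.1 and 0.2, under the population split, common risk and independent episodes assumed above. Covariate adjustment is not reflected in these figures.

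A reader might go further and conclude that the before-after and group-by-year comparisons are distorted to the same degree. The documents do not support that: stable area differences cancel in those contrasts, so any inflation depends on area-by-year variation, for which no figure is given. Should-fix: the primary inference is affected, but specification and reporting can deal with it.

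**What to change.** In Design and Data analysis:

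1. Describe the study as a controlled before-after study with one treated area.
2. Make the primary effect the treated-area-by-programme-year interaction in a logistic model with area and year as fixed effects and a patient random intercept or patient-clustered SE. The two years of episodes already planned suffice.
3. Say openly that this replaces the concurrent-only contrast, which cannot be estimated once area is a fixed effect.
4. State that the interval is conditional on these three areas and two years, and also show it for area-by-year SDs of 0.05, 0.1 and 0.2.
5. If earlier years can be drawn from the unit's records (the documents do not say), show the same contrast for them as placebo years. Their raw spread already contains sampling error. If it is used to set the interval, either use it in place of the model SE or subtract its sampling variance first. A few years give only a rough SD.

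Cost: revised wording and, optionally, one further extraction of routine records. The intervention and the planned data collection do not change. The price is precision: an SE of about 0.275 instead of 0.195 before any area-by-year variance is added.

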The present study will be carried out in the MHHU of the Regional University Hospital (RUH) of Malaga, a public hospital of the Andalusian Health Service. In addition to the Mental Health Clinical Management Unit of the HRU of Málaga, this MHHU is a reference for two other regional hospitals in the province of Málaga: The Málaga East Axarquía Hospital and North Málaga Health Management Area. The Mental Health Clinical Management Unit of the RUH of Malaga, according to figures from the 2022 database of users, serves a reference population of 336,968 people, while 150,823 people depend on the Mental Health Clinical Management La Axarquía and 109,958 depend on the Mental Health Clinical Management North of Málaga, resulting in a reference population of 597,749 people for hospitalization resources.

The MHHU has 40 beds in double rooms and is divided into two functional units. The access routes to hospitalization in this unit are admission from the Emergency Services, after evaluation by a psychiatrist, and programmed admission from another unit. The average occupancy rate is two thirds (28 beds) of the total capacity and the average stay in the year 2022 was 13.7 days, with a total number of admissions of 838. The data collected at the RUH of Malaga indicate an early readmission rate of 15.08% in the year 2022, using a time reference of 30 days until readmission.

The Spanish public health system is functionally organized into levels, with Primary Care comprising the first level and Ambulatory Specialized Care and hospital Emergency Services comprising the second level of care. The third level of care consists of hospital units with a high degree of specialization. The proposed intervention will primarily take place in the hospitalization unit (third level), as well as in the community-based outpatient care facilities

affiliated with said hospital, including the North Guadalmedina and Central Malaga Community Mental Health Units (second level).

- **Intervention and control group**

Intervention group

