The intervention program is based on the Discharge Transition Model for the prevention of hospital readmission in Mental Health. For its development, a multidisciplinary readmission commission was established, comprised of professionals from various categories and from different Mental Health facilities. The aim was to address this issue in detail and actively participate in the review of available evidence and decision-making regarding the development and implementation of the current program.

This is a multicomponent program that initially involves the development of a scale to assess the risk of readmission for each patient, followed by its systematic application. This allows for stratification of patients according to their risk of early readmission and adaptation of the intervention to the needs of each risk level. The intervention includes elements aimed at promoting continuity of care after discharge, transitioning back to the community setting, as well as elements aimed at enhancing personal and emotional resources through psychotherapeutic approaches. The following describes the different components of this intervention program.

Construction of the Early Readmission Risk Scale

For the preliminary analysis of risk factors associated with readmission, a retrospective observation will be conducted. This will involve analyzing all episodes from the previous calendar year stored in the database of the MHHU of the RUH of Malaga, provided that the records are complete. "Cases" will be selected from episodes that resulted in readmission within 30 days post-discharge, while an equivalent number of "controls" will be randomly selected through simple random sampling. Following this analysis, a measurement instrument will be developed to determine the risk of early readmission for all patients admitted to the MHHU.

A literature search was conducted to identify variables that have been associated with readmission and early readmission in other populations. The following variables were selected

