for analysis in the reference population: Sociodemographic factors (sex, age, marital status, legal incapacity, employment status, criminal history, and social functioning), psychiatric history (previous admissions, emergency service visits in the twelve months prior to admission, history of suicide attempts, attendance at community nursing follow-ups in the six months prior to admission, and somatic comorbidity), reasons for admission (presence of hetero- or auto-aggression or deficits in self-care), clinical characteristics (primary diagnosis, substance use, non-adherence to follow-up in the previous 12 months, and non-adherence to treatment up to one month before admission), admission characteristics (urgent or scheduled access route and length of stay), and discharge measures (coordination with referring physician in the CMHU and prescription of depot medication).

During admission to the hospitalization unit, all users must have the aforementioned Early Readmission Risk Scale of the MHHU of the RUH of Malaga administered. This will allow for the classification of patients according to their risk level, establishing defined cutoff points, resulting in three categories: Patients at low risk, medium risk, and high risk. This scale will be completed by the referring physician during the initial assessment interview upon admission to implement the proposed measures for each risk level. Additionally, the referring physician will establish contact with the case management figure responsible for the program for the referral of cases with a score indicative of a high risk of early readmission or patients with early readmission within 30 days post-discharge.

Intervention measures based on the risk of early readmission

For patients classified in the low-risk group, general measures would be applied. For patients in the medium-risk group, reinforced measures would be implemented. Lastly, for patients considered to be in the high-risk group, intensive case management measures would be applied, and if they meet the inclusion criteria, they would be included in the Post-Discharge Group Psychotherapeutic Intervention.

1. General measures

The following measures would be applied to patients with a low risk of readmission:

-Ensure coordination between physicians during admission and a follow-up appointment within 7 days.

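### No independent validation set is named for the readmission risk scale, and the only planned accuracy test appears to reuse the sample that builds it

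*Combined protocol and SAP*

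**What the plan says.** Testing the scale is a stated purpose. The secondary aims include "To test whether a scale for estimating the risk of early readmission has adequate psychometric characteristics for such estimation", and the Design section adds a study to "assess the predictive value and validity of the early readmission risk rating scale". Neither place gives a population, accuracy measures or a threshold for adequacy.

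On development, the section on constructing the scale describes "analyzing all episodes from the previous calendar year stored in the database of the MHHU of the RUH of Malaga", where records are complete. All 30-day readmissions are taken as cases, with an equal number of randomly sampled controls. Under Data analysis, "a forward stepwise multivariate analysis will be performed, introducing variables with greater statistical significance". The scale is then one "whose sensitivity and specificity will be tested beforehand using a receiver operating characteristic (ROC) curve". No split sample, resampling, calibration or later-year test is mentioned.

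On use, the plan says "all users must have the aforementioned Early Readmission Risk Scale of the MHHU of the RUH of Malaga administered". Care then follows the score: general measures for low risk, reinforced for medium risk, and "for patients considered to be in the high-risk group, intensive case management measures would be applied".

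On the control areas, the Setting section says "this MHHU is a reference for two other regional hospitals in the province of Málaga". Patients from those two areas are excluded from the programme and keep usual treatment. The Data analysis section lists the scale's variables among the confounders in the comparison between intervention and control groups.

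**The concern.** Two sources of data come to mind for judging the scale, and each would misjudge it.

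The first is the development sample. If one small sample selects the items, fits the weights and supplies the ROC curve, the curve partly measures fit to noise, and the scale looks better than it will prove in new patients. Half of that sample are cases by design, so positive and negative predictive values taken from it describe a population with 50% readmission, not 15%.

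The second is the RUH-area patients in the programme year. Their score triggers care intended to prevent the very outcome being predicted, so a correctly flagged patient who is helped counts as a false positive. Accuracy of the scale and effect of the programme are then mixed.

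At stake is the secondary aim on the scale's psychometric adequacy. With no population fixed in advance, the reported accuracy would depend on a choice made after the data are seen.

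**Working it through.** The plan states no target AUC, expected accuracy or sample size, so there is no design figure to reproduce. The checks use its own counts plus stated assumptions.

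**Inputs from the Setting section.** 838 admissions in 2022; early readmission rate 15.08%; catchments of 336,968 (RUH), 150,823 (Axarquía) and 109,958 (North Málaga), which sum to 597,749 as stated. I assume that the development year is 2022 and that all records are complete.

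**1. Size of the development sample.**
- Cases: 838 × 0.1508 = 126, plus 126 controls. Incomplete records would lower this.
- Candidates: 7 sociodemographic, 5 psychiatric history, 4 clinical, 2 admission and 2 discharge variables, plus 1 to 3 for reasons for admission depending on coding. That is 21 to 23; I use 22.
- Cases per candidate: 126 / 22 = 5.7.
- Every eligible case of the year is used, so none is left for an independent test in that year.

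**2. Optimism of the development ROC.** Simulation: 838 episodes, all cases plus equal controls, forward stepwise entry at p < 0.05 (assumed; the plan gives no entry rule), 80 replicates per setting.

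| Candidates | Predictor effects | Apparent AUC | True AUC | Excess |
|---|---|---|---|---|
| 22 | weak | 0.652 | 0.565 | 0.09 |
| 22 | moderate | 0.733 | 0.673 | 0.06 |

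Over 15 to 30 candidates the excess runs from 0.05 to 0.10.

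**3. Predictive values in a 1:1 sample.** PPV = sens × π / [sens × π + (1 − spec) × (1 − π)]. With sensitivity and specificity of 0.70 (assumed):
- π = 0.50: 0.35 / (0.35 + 0.15) = 0.70.
- π = 0.1508: 0.1056 / (0.1056 + 0.2548) = 0.29.

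**4. Accuracy in programme patients.** Logistic risk model with a normally distributed score, mean risk 15.08%, true AUC 0.70, risk groups in equal thirds. Risks are multiplied by the risk ratio (RR) of each group and the AUC recomputed. All AUCs, group sizes and effects are assumptions.

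| RR low / medium / high | Observed AUC | High-risk PPV |
|---|---|---|
| 1 / 1 / 1 | 0.700 | 26% |
| 0.8 / 0.8 / 0.8 | 0.693 | 21% |
| 0.6 / 0.6 / 0.6 | 0.687 | 16% |
| 0.8 / 0.7 / 0.6 | 0.659 | 16% |
| 1 / 0.9 / 0.7 | 0.652 | 18% |
| 1 / 0.85 / 0.6 | 0.633 | 16% |
| 1 / 0.75 / 0.5 | 0.612 | 13% |

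High-risk PPV falls under any benefit in that group. AUC falls materially only when the relative benefit rises with risk. If the benefit were larger at low risk (0.7 / 0.85 / 1), AUC would rise to 0.731.

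**5. What the control areas could support.** Share of the catchment: (150,823 + 109,958) / 597,749 = 260,781 / 597,749 = 43.6%. Episodes: 838 × 0.436 = 366. Readmissions: 366 × 0.1508 = 55, leaving 311 without. This assumes admissions proportional to population and the same readmission rate in each area.

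Hanley-McNeil at A = 0.70: Q₁ = A/(2 − A) = 0.538; Q₂ = 2A²/(1 + A) = 0.576.
Variance = [0.21 + 54 × (0.538 − 0.49) + 310 × (0.576 − 0.49)] / (55 × 311) = 0.00173 (unrounded Q values).
SE = 0.042; 95% half-width 1.96 × 0.042 = 0.08. At true AUC 0.65, 0.75 and 0.80 the half-widths are 0.084, 0.078 and 0.073. Episodes are treated as independent; repeat admissions of one patient would widen these.

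**The case against.** A reader might infer that the scale will look falsely poor where it is used, because no untreated data exist to test it. The documents do not support that, for three reasons.

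First, untreated data do exist. Control-area patients are admitted to the same unit, are outside the programme and keep usual treatment. The set is unnamed, not missing.

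Second, nothing in the plan says that validity will be judged in treated patients. The one accuracy test specified uses pre-programme data, where the likely error is in the other direction. Even in treated patients the loss of AUC depends on effects graded by risk: at true AUC 0.70 there is none if the programme does nothing, and it is under 0.01 for a uniform 20% reduction. A fall in PPV reflects fewer events and is not in itself poorer ranking.

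Third, a reader might infer that risk-factor estimates are also attenuated by treatment. The only risk-factor analysis described uses episodes from before the programme, so this does not follow.

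These points stand, and they make the programme-patient distortion conditional. They do not remove the gap. It can also be said that the plan never states outright that the ROC uses the case-control sample. That is true, but no other data set is described. Running it on all episodes of that year would repair the prevalence but not the optimism, since the cases would be the same ones.

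The proposed validation set has limits too: a half-width of about ±0.08 is as wide as most of the biases at issue, the catchment differs, and a shared ward makes contamination possible.

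**Conclusion.** The concern holds in this form: a validity study is promised, no independent set is named for it, and the only accuracy test described appears to reuse the development sample. Followed as written, the plan yields optimistic AUC, sensitivity and specificity (AUC too high by roughly 0.05 to 0.10 under the simulated settings), and predictive values that do not apply at a readmission rate of about 15%.

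The distortion in programme patients is a conditional second hazard, to be excluded in advance rather than predicted. With true AUC 0.70, equal thirds and low-risk RR of 1.0, AUC would appear as 0.65 to 0.61 for high-risk RRs of 0.7 to 0.5. The documents give no effect sizes, cut-offs or expected AUC, so these figures are illustrative.

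One secondary aim is affected. The primary readmission comparison is not. The change is worth making because the better data are already within the trial.

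**What to change.** Add one paragraph to Data analysis:

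- Freeze the items, weights and cut-offs before the programme starts.
- Correct the development-sample ROC for optimism by bootstrap, repeating the whole stepwise selection in each resample. Do not report predictive values from the 1:1 sample unless they are re-weighted to the true readmission rate.
- Name the implementation-year control-area admissions to the MHHU as the usual-care validation set. Compute scores from the scale variables already needed as covariates. Report AUC, calibration, and sensitivity, specificity and PPV at each cut-off, with intervals that allow for repeat episodes.
- Report RUH-area results separately as performance under the programme, and do not use them to judge the scale.

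Reconcile two statements: that all users of the unit are scored, and, in the Abstract, that the programme is not implemented for the control hospitals. It is unclear whether control patients receive a score. Computing scores from covariates works either way, but whether treating physicians see them bears on contamination.

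The cost is one paragraph and no new variables. Limits to state: about 366 episodes and 55 events under the assumptions above, AUC SE about 0.042, a catchment other than the intervention area, the shared ward, and possible overlap of patients with the development year, since the previous-year database covers the same unit.
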